**9-Sep-2018**

### PROTOCOL VERSION HISTORY

Version	Date (dd-mmm-yyyy)
Initial	9-Sep-2018
Amendment	N/A

### ETHICS AND REGULATORY COMPLIANCE STATEMENT

The procedures set forth in this protocol are designed to ensure that the sponsor(s) and principal investigator(s) abide by the International Conference on Harmonization (ICH) current Good Clinical Practice (cGCP) guidelines, current Good Laboratory Practice (cGLP) guidelines, the Declaration of Helsinki, and applicable local regulatory requirements and laws in the conduct, evaluation, and documentation of this study.

Protocol Name	Laser Analgesia
Protocol Number	
Investigational Product Name	Laser Analgesia in Cavity Preparations
Date: (dd-mmm-yyyy)	06-Sept-2018
Author	[name]

## PROTOCOL HISTORY

Version	Date (dd-mmm-yyyy)	Description
V1	06-Sept-2018	Initial Release
V2		

## SYNOPSIS

Title of Study	Clinical Study of Laser Analgesia in Cavity Preparations using the Er,Cr:YSGG Laser
Objectives	To show there is laser analgesia. Restorative dental procedures potentially can be performed without needle injection first.
Planned Number of Subjects and Duration of Involvement	The planned number will be forty-eight patients. The duration will last till all patients are done.
Patient Population	Patients included in the study are adults 19-65 years old who had at least two cavity preparations of the same type, with the same approximate size lesion. Excluded patients include children, people with language barriers, pregnant women, immune compromised patients compromised (No bronchitis, no sinus infection, no ear infection, ect...), patients with heart disease, uncontrolled hypertension, cardiac arrhythmia, and patients whose teeth amalgam restorations were in close proximity to the lesion.
Investigational Product Name	Clinical Study of Laser Analgesia in Cavity Preparations using the Er,Cr:YSGG Laser
Methodology Overview	The study involves using the Er,Cr:YSGG Laser to perform cavity preparation without giving any injection anesthesia. This study is going to be done to show there is laser analgesia.

## **ABBREVIATIONS**

---

US/USA                    United States of America

## **LIST OF FIGURES**

**No table of figures entries found.**

## 1 INTRODUCTION

General dentistry can be stressful to both the patient and the doctor due to the fear of the needle before most dental procedures. One of the main benefits of using Lasers is pain reduction and anti-inflammation. In some of the references, scientists use electrodes inserted in the brain of cats or rabbits. They have also placed electrodes in the pulp of teeth to measure action potentials as pain is perceived or attenuated. They were able to show that pain causes action potential formed and pain reduction (analgesia) causes diminishing effects on the action potential. However, this is not practical in human study. Using the Visual Analog Scale (VAS) is a good way in gauging the patient's experience of the procedures. Small, medium, and large sized cavity preparations all to be measured. Effort is made to standardize the amount of cutting with each technique. The study is aimed to show if there is Laser Analgesia and if the use of Low Level Laser Therapy makes a difference in providing better analgesia.

## 2 DESCRIPTION OF THE INVESTIGATIONAL PRODUCT

### 2.1 Overview

Lasers have been used in several areas of medicine for a long time, even becoming a standard of care for many medical specialties, ophthalmology, dermatology, urology. In dentistry, the clinical use of lasers began in the 1980s. In search of the ideal wavelength for all dental needs, several manufacturers developed different systems and each had their own benefits and limitations. Overtime and research, it has been understood how these different lasers act on the bio-physical aspect, and that there wasn't one laser that could answer all our needs in dentistry [3]. Lasers work by emitting a wavelength of high energy light, which when focused on a certain skin condition that will create heat and destroy diseased cells. These lasers have a very high affinity for tissues containing water. Work performed by Ohshiro and Calderhead showed that an Er:YAG laser can be used to achieve laser analgesia based on the concept that Low Level Laser Therapy (LLLT) may occur simultaneously with high level laser treatment [1]. Laser analgesia does not produce a profound lack of sensation as is the case with using an injection anesthesia. It has been shown in *vivo* studies that LLLT can produce an analgesic effect on nerves that innervate the oral cavity by using a near or middle infrared laser [2, 3, 11, 12, 13, 14, 15]. It is theorized that LLLT decreases the firing frequency of nociceptors (pain receptors), particularly the afferent axons from nociceptors that are of low velocities. The LLLT affects only selective target fibers. As a result, The LLLT produces an analgesic effect, but not an anesthetic effect.

Laser specific to this study is Er,Cr:YSGG (Erbium, Chromium: Yttrium, Scandium, Gallium, garnet) which is a waterlase iplus laser from Biolase, Inc. Irvine, CA. This laser is the markets best-selling all-tissue laser that is minimally invasive and used for dentistry. It features expanded and enhanced capabilities such as the Surefire delivery system and REPAIR protocols to give patients the best experience and for practice growth. Waterlase

iplus offers complete versatility across all tissue types. It is engineered to provide a refreshing, comfortable patient experience when compared to traditional tools. It is cleared for over 80 different indication for soft tissue, hard tissue and bone. This is more than any other dental laser out there. Waterlaser iplus leads to results by empowering dentists to offer the best possible dental experience with single-visit, multi-quadrant, minimally invasive dentistry. This system is reliable, durable and flexible for any dental practice.

Er, Cr:YSGG laser system (2790nm, middle infrared) for cavity preparation and caries removal without the need of injection is one of the most attractive advantages of using the laser [4 , 5, 16, 17, 18, 19]. Due to the plentiful amount of water and air cooling in the Er:Cr:YSGG laser, there is no temperature change on the surface.[6] There is already the benefit of no side effect of heat on the surface of treatment. Different techniques are being used to achieve cavity preparation with the Er:Cr:YSGG laser system with no injection anesthesia [7]. The results claimed by using the different techniques are generally presented based on anecdotal evidence. One group of users may use one setting, typically at higher power levels, to perform the entire cavity preparation. A few of these high power examples are 6 Watts at 20 Hz, 4.5 Watts at 15 Hz, or 3 Watts at 10 Hz. Another group of users may use a moderate power setting to perform the entire cavity preparation such as 4.5 Watts at 20 Hz, 3.5 Watts at 15 Hz, or 2.5 Watts at 10 Hz and the setting is used. A third group of users use different settings for each step of the cavity preparation. They start out using relatively lower power such as 2 Watts, 30 Hz at a new lesion on the occlusal surface. The power is incrementally raised over time until ablation of the tooth takes place. After the cavity is removed, a lower power setting is used to finish and smooth the final preparation. The setting used is 2 Watts at 30 Hz. The users of these different techniques all claim they could perform cavity preparations without giving injection anesthesia and the patients are comfortable.

Because of the multiple variables involved in cavity preparation and causes of discomfort, the study will focus on specific parameters that may induce an analgesic effect. There are multiple variables in choice of power and frequencies that different users select for cavity preparation. In this study, we will focus on specific parameters and cavity preparations in small lesions (1.5mm X 1.5mm X 2mm) and in medium (2mm X 2m X 2.5mm) / large lesions (3.5mm X 2.5mm X 3mm ).

## 2.2 Proposed Intended Use Statement

The intended use is to find out if there is laser analgesia and if LLLT makes a difference in providing better analgesia to patients.

## 3 STUDY OBJECTIVES

The principal objective of this study is to prove the phenomenon of laser analgesia. Traditionally before a cavity preparation is performed, the doctor will use local anesthetic (Needle Injection) before using rotary instrument to do a cavity preparation. The study involves using the Er,Cr=YSGG Laser to perform cavity preparation without giving any injection anesthesia. VAS (Visual Analog Scale) will be used to have patients rate the laser

cavity preparation procedure to show there is laser analgesia. On each patient subject that has two similar size cavities of the same classification, either Class I or Class V, on similar teeth. Two different laser protocols will be used. One includes Low Level Laser Therapy (LLLT) to condition the pulp producing analgesia before using higher power to perform the cavity prep. The other protocol will skip the LLLT setting and prepare the cavity with the higher power to perform the cavity prep. The design of the study is to find out if there is laser analgesia and if LLLT makes a difference in providing better analgesia. The VAS forms from each procedure will be used to show there is laser analgesia and potentially cavity preparations can be performed by using the laser without the need to give injection anesthesia first.

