#### **6.1.2 Safety issues**

If patient complains of having pain, raising hand signal, injection anesthesia will be given as an option to finish the procedure but will not be included in the study.

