## 7 STUDY PROCEDURES

### 7.1 Workflow

This study will consist of two procedures. Both procedures will be performed on the same patient. Both procedures are cavity preparations. The tooth is chosen and the first procedure is started. The first one will be done with LLLT protocol prior to using the higher power to perform the cavity preparations. The second preparation will be done without LLLT first and thus using the higher power laser for cavity preparation from the beginning.

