#### **Laser Preconditioning:**

- A. Laser Desensitization/ preconditioning procedure
  - a. Randomly select one tooth to have laser preconditioning performed on it
    - Preconditioning is using some LLLT on the tooth without expecting much, if any, ablation of the tooth.
    - For preconditioning, the setting is 0.25 Watt, 50Hz, 0% water, 0% air, H mode.
  - b. Aim fibre-optic tip perpendicular to the surface of cervical portion of tooth
  - c. Ensure that a 2mm distance between the end of the fiber optic tip and the surface is maintained
  - d. Go back and forth with the fibre-tip over a 2mm line for the number of seconds indicated
  - e. Prep the cavity on the first tooth (settings to follow)
  - f. Prep the cavity on the second tooth, without laser preconditioning

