## **9.3 Planned Analyses**

The clinical study report will contain only information necessary to prove this phenomenon.

Statistical analysis will include the VAS forms from each procedure which will be used to show there is laser analgesia and potentially cavity preparations can be performed by using the laser without the need to give injection anesthesia first. The VAS form is used to show how much pain they are in and if any. All patient data will remain anonymous during analyses to maintain patient confidentiality.

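### The principal objective is to prove laser analgesia from VAS scores, but both teeth are laser-prepared, so only the added effect of LLLT can be estimated, and that effect is confounded with order

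*Protocol*

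**What the plan says.** The synopsis gives the objective as "To show there is laser analgesia". Protocol section 3 goes further ("The principal objective of this study is to prove the phenomenon of laser analgesia") and names the evidence: "The VAS forms from each procedure will be used to show there is laser analgesia". Section 11.2 repeats the expectation of proof. Section 9.3 again assigns the VAS forms to this purpose, and opens with "The clinical study report will contain only information necessary to prove this phenomenon".

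Sections 3, 4.1, 5.1.4 and 7.1 describe two procedures per patient. Both are laser cavity preparations, and they differ only in whether LLLT preconditioning comes first. Injection followed by rotary preparation appears in section 3 as the traditional approach, not as a study condition. The VAS rule in section 4.1 is relative: a lower average marks the better treatment.

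The tooth that receives LLLT is chosen at random (4.1 and 7.1). The sequence is fixed. Section 7.1 says of the two preparations "The first one will be done with LLLT protocol prior to using the higher power to perform the cavity preparations", and its step list ends with "Prep the cavity on the second tooth, without laser preconditioning".

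Two rules affect the scores themselves. Section 4.1 assigns an overall VAS of zero to a patient who never raises a hand. Section 6.1.2 says "injection anesthesia will be given as an option to finish the procedure but will not be included in the study".

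**The concern.** A low VAS on a laser-prepared tooth can mean that the laser dulled the pain, or that this lesion would have hurt little anyway. Separating the two needs a preparation without the laser effect, or at least a justified reference level. The protocol has neither, so the conclusion it is written to reach would be unsupported whatever the data show.

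The LLLT contrast does not fill the gap. A lower VAS with LLLT would be some evidence of a laser effect. An equal VAS could not count against laser analgesia, because section 2.1 adopts the idea that "Low Level Laser Therapy (LLLT) may occur simultaneously with high level laser treatment", so the comparison tooth may receive the effect too. With order fixed, a difference in either direction may also come partly or wholly from being first or second.

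The opening of 9.3 adds a reporting risk. Taken literally, it would let results that do not support the phenomenon be left out.

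**Working it through.** **1. The plan's own figure.** Section 9.1 uses n = c²Np(1−p) / [A²N + c²p(1−p)] with c = 1.96, N = 50, p = 0.50, A = 0.025.
- Numerator: 3.8416 × 50 × 0.25 = 48.02.
- Denominator: 0.000625 × 50 + 3.8416 × 0.25 = 0.03125 + 0.9604 = 0.99165.
- n = 48.42, as stated.

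The printed line has 1.69 in the numerator, which would give 36.00. This looks like a typing slip and does not bear on the present point. What does bear on it is that the formula sizes a single proportion. It contains no VAS difference and no SD.

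**2. What the VAS means can identify.** Let S be mean VAS without any laser analgesia, L the analgesic effect shared by both teeth, D the added effect of LLLT, and T the extra pain on the second tooth due to order.
- LLLT tooth (first): S − L − D
- Other tooth (second): S − L + T
- Difference, other minus LLLT: D + T

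S and L enter only as S − L. With D = 10 and T = 0 (illustrative values):

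| S | L | LLLT tooth | Other tooth | Difference |
|---|---|---|---|---|
| 20 | 0 | 10 | 20 | 10 |
| 40 | 20 | 10 | 20 | 10 |
| 60 | 40 | 10 | 20 | 10 |

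The data are identical whether the shared effect is 0, 20 or 40 mm. More patients would not change this.

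**3. Order.** The tooth is randomised but the sequence is not, so the paired difference estimates D + T. To show what that could do, take a two-sided 5% paired t-test with noncentrality (D + T)/(SD/√n). The protocol gives neither an SD nor an order effect, so both are assumed: n = 48 complete pairs, D = 0, SD 20 mm (range 15-25). The noncentrality at T = 5 mm and SD 20 mm is 5/(20/√48) = 1.73.

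| Order effect T | False significant result in the direction of T (SD 20; range for SD 25 to 15) |
|---|---|
| 0 mm | 2.5% each way |
| 2 mm | 10% (8-15%) |
| 5 mm | 40% (27-62%) |

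The sign matters. T = +5 mm favours LLLT; T = −5 mm goes against it with the same probability. If LLLT truly helps by 10 mm, T = −5 mm lowers power from 92% (78-99%) to 40% (27-62%). With order randomised 24/24, T cancels on average, and simulation under the same model gave false-positive rates of 1.9-2.3% in each direction.

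**4. Precision of the contrast.** The 95% CI half-width is t × SD/√n. At SD 20 mm it is 5.8 mm for 48 complete pairs (4.4-7.3 mm for SD 15-25) and 6.4 mm for 40 pairs.

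**5. The VAS definition.** Section 4.1 asks every patient for a final overall mark and, in the same paragraph, assigns zero to those who never raise a hand. The matching text in 7.1 asks for the final mark and has no zero rule. Sections 4.1 and 7.1 take a VAS mark before anaesthetic is offered, whereas 6.1.2 can be read as removing the teeth then finished under injection. The zero rule, and 6.1.2 on that reading, can lower the mean VAS whatever L is.

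**The case against.** Four points deserve weight.

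*The protocol also asks a neutral question.* Sections 1 and 2.2 and one sentence of section 3 ask whether there is laser analgesia and whether LLLT makes a difference. This stands, but the first half of that question meets the same obstacle. A reader might go further and infer that the design says nothing about laser analgesia. That is too strong: the two-tooth contrast can in principle show an effect of preconditioning, and completion without injection can be described without a comparator.

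*Section 9.3 may intend only data minimisation.* A reader might infer that the protocol plans a one-sided report. The documents do not support that. The next sentence of 9.3 brings in the VAS forms from each procedure, section 4.1 has each patient's data and the hand raises recorded and analysed, and 12.7 commits to good publication practice. The fault lies in one sentence.

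*Low scores on both teeth need not be presented as proof.* The only stated rule for interpreting VAS is comparative, and no absolute threshold is given. That is fair. But sections 3 and 9.3 do say the forms will show laser analgesia, so the risk comes from the text.

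*The percentages rest on assumed inputs.* This stands in full. Nothing in the protocol supports a 5 mm order effect or its direction, and many zero scores under the 4.1 rule would make the paired normal model a poor description.

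**Conclusion.** The principal objective cannot be met by the data that the protocol collects. An analgesic effect common to both teeth is not identifiable, and no analysis plan could repair that. This core problem has no numeric size; the 10 and 20 mm example only shows that the same data fit a shared effect of 0 or 40 mm.

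The one estimable quantity, the added effect of LLLT, is confounded with order because the LLLT tooth always comes first. The figure of 40% (27-62%) applies to order alone. It holds for 48 complete pairs, SD 20 mm (15-25) and an order effect of 5 mm, all assumed. It should not be read as the size of the main problem, nor as evidence that an order effect exists. Nor should the fixed sequence be taken to mean that LLLT is allocated without randomisation: the tooth is randomised, the order is not.

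The 9.3 point is secondary, a sentence that would permit selective reporting if followed alone. The objective and the order need correcting before the trial can support a conclusion.

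**What to change.** 1. **Objective.** In section 3, with the synopsis, 9.3 and 11.2 to match, make the primary objective the estimation of the within-patient difference in overall VAS between preparation with and without LLLT preconditioning. Present absolute VAS level and completion without injection as descriptive, and drop the language of proving or showing laser analgesia. Sections 1 and 2.2 can stay.
2. **Order.** In 7.1, randomise which preparation is done first as well as which tooth receives LLLT.
3. **Reporting.** Replace the first sentence of 9.3 with a commitment to report all VAS, hand-raise and anaesthetic-use results whatever their direction, for every treated tooth whose data are retained. The limit is needed because Table 1 in 5.3 has the data of patients who withdraw before collection is complete returned or destroyed. State the number withdrawn.
4. **Data handling only.** Reconcile the zero rule in 4.1 with the final overall mark in 4.1 and 7.1 by using the patient's own final mark. Reconcile 6.1.2 with 4.1 and 7.1 so that teeth finished under injection stay in the data, flagged, with the pre-injection VAS mark kept. Add a stated rule for their primary value, since overall VAS is marked only after the preparation ends.
5. **Sample size.** In 9.1, say that the formula sizes a single proportion and not this contrast, and give the expected precision under a stated SD and number of complete pairs (step 4 of the working shows the form).

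The cost is a narrower claim, wording changes in the sections named, and one more random allocation per patient. No new arm, patients or visits are needed. Whether 48 patients give enough precision becomes a visible question.

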## 4 STUDY OVERVIEW

### 4.1 Study Approach

[figure not shown]
**Treatment.** Preconditioning and cavity preparation are done using the Er:Cr:YSGG laser, Waterlase MD (mfg: Biolase Technology Inc, Irvine CA), and the gold hand piece with an MG6 fiber tip, trunk fiber, contra-angle hand piece. *Preconditioning.* Preconditioning is preformed using laser desensitization. One tooth will be randomly selected, and preconditioning will be performed using LLLT on the tooth with minimal tooth ablation. The LLLT settings that will be used for preconditioning are 0.25 Watts, 50 Hz, 0% water, 0% air, H mode. Following this a fiber-optic tip will be aimed perpendicular to the surface of the cervical portion of the tooth, ensuring that a 2mm distance will be maintained between the end of the fiber optic tip and the surface. The fiber-tip will be used to generate a 2mm line. The cavity on the second tooth will be prepared for without laser preconditioning. *Lesion Preparation – small preparations.* Small preparations are to be performed as follows. The Waterlase MD is set to 4.5W, 15 Hz, 65% air, and 60% water and the cavity is prepared according to the preferred technique. If patients indicate sensitivity, the procedure will be halted, patients fill out the VAS form and anesthetic will be offered. For patients who refuse anesthetic, the procedure will be continued at the same settings. *Lesion Preparation – small to medium preparations.* Small to medium preparations will be performed as follows. The Waterlase MD will be set to 2W, 15 Hz, 65% air, and 60% water and the cavity will be prepared according to the preferred technique. If patients indicate sensitivity, the procedure will be halted, patients fill out the VAS form and anesthetic will be offered. For patients who refuse anesthetic, the procedure will be continued at the same settings.

**Restoration.** *Overall VAS Score.* Up to 3 intra-operative VAS measurements are recorded. If a patient feels even the slightest amount of pain during the procedure, they will be instructed to raise their hand and the treatment will be paused. The patient is then asked to fill in the VAS form before the procedure will be continued. After conclusion of the cavity preparation, patients will be asked to mark one last VAS rating indicating the overall pain of the procedure. Patients that do not raise their hand throughout the entirety of the procedure will be given an overall VAS rating of zero. Data for each patient will be recorded and analyzed in this way.

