#### **Preparation of Lesion:**

- A. Laser ablation- Small Preparation
  - a. Waterlase MD settings: 4.5W, 15Hz, 65% air, 60% water
  - b. Prepare cavity preparation using preferred technique
  - c. If the patient indicates sensitivity,
    - Halt the procedure
    - Have the patient mark the VAS form,
    - Offer anaesthetic; if refused, continue using the same settings
- B. Laser ablation- Small and Medium Preparation
  - a. Waterlase MD settings: 2W, 15Hz, 65% air, 60% water
  - b. Prepare cavity preparation using preferred technique
  - c. If the patient indicates sensitivity, either
    - Halt the procedure

- Have the patient mark the VAS form,
- Offer anaesthetic; if refused, continue using the same settings

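### When an injection is accepted on the first (LLLT) tooth, the protocol does not settle which pain marks count, so a second tooth prepared under residual anaesthetic may enter as laser data

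*Protocol*

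**What the plan says.** Each patient has two similar cavities prepared by laser, and Section 7.1 treats these as two procedures. On order it says "The first one will be done with LLLT protocol prior to using the higher power to perform the cavity preparations" and then "The second preparation will be done without LLLT first". Chance decides only which tooth is preconditioned: "Randomly select one tooth to have laser preconditioning performed on it". The next step after the first preparation is "Prep the cavity on the second tooth, without laser preconditioning", with no condition or interval between the two.

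When the patient signals sensitivity, Sections 4.1 and 7.1 halt the work, have the VAS form marked, and then: "Offer anaesthetic; if refused, continue using the same settings". Only refusal has a stated continuation there. Acceptance is covered in Section 6.1.2: "injection anesthesia will be given as an option to finish the procedure but will not be included in the study".

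The overall score comes at the end of the preparation: "After conclusion of the cavity preparation, patients will be asked to mark one last VAS rating indicating the overall pain of the procedure". Section 4.1 also gives an overall rating of zero to a patient who never raises a hand, and says that every patient's data are recorded and analysed in this way. It counts and analyses hand raises, and judges the mode of treatment by its average score.

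**The concern.** The study aims to measure pain during laser preparation without injection and to compare teeth with and without LLLT. An accepted injection interrupts that measurement in the patients who reported pain. Three things then need a rule, and the protocol gives none that is consistent:

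- what the overall mark on the injected tooth stands for;
- what is left out of the study;
- what happens to a second tooth prepared afterwards.

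The second tooth matters most because it is always the no-LLLT control. If it is prepared while anaesthetic from the first tooth still acts, low scores and absent hand raises would be credited to the laser alone, and the automatic zero would make this look like painless laser treatment. If the protocol instead means to drop such patients, those with the most pain leave the comparison. In either case the average pain reported for injection-free laser preparation no longer describes all enrolled patients.

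**Working it through.** The protocol states no injection rate, VAS mean or SD, so there is no figure of its own to reproduce on this point. The check follows the order of events, then sizes the effect under stated assumptions.

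**1. Order of events, injection accepted on tooth 1 (LLLT)**

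| Event | Relation to the injection |
|---|---|
| VAS mark at the halt, tooth 1 | before; valid as laser pain |
| Overall VAS, tooth 1 | after; covers laser pain before the injection and preparation under it |
| VAS marks, hand raises and overall VAS, tooth 2 (no LLLT) | after; affected only if the anaesthetic still acts on that tooth |

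**2. What Section 6.1.2 could leave out**

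| Unit left out | Tooth 1 | Tooth 2 | Result |
|---|---|---|---|
| Nothing (Section 4.1 as written) | all kept | kept | mixed overall mark, and tooth 2 possibly too low |
| Later marks on that tooth | halt mark kept | kept | tooth 2 possibly too low |
| The injected procedure | dropped | kept in the no-LLLT average | painful LLLT teeth lost, and tooth 2 possibly too low |
| The patient | dropped | dropped | no post-injection mark analysed, but exclusion depends on pain |

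Section 7.1 calls each preparation a procedure, and Section 6.1.2 speaks of finishing the procedure. Read together, the exclusion most naturally reaches tooth 1 and no further.

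**3. Size, if tooth 2 is kept and the anaesthetic reaches it**

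Shift in the mean no-LLLT VAS = share injected on tooth 1 × tooth-2 VAS lost. Assumed ranges are 10% to 30% and 30 to 50 mm.

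- Low end: 0.10 × 30 mm = 3 mm
- High end: 0.30 × 50 mm = 15 mm

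The automatic zero makes a near-complete loss possible where the tooth is numb and no hand is raised.

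**4. Cross-check by simulation**

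The assumptions are VAS means of 20 (LLLT) and 30 (no LLLT), between- and within-patient SDs of 12 each, scores limited to 0–100, and injection accepted by the highest scorers on tooth 1. Tooth-1 scores are left unaltered. The true LLLT minus no-LLLT difference is −9.3 mm.

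| Injected on tooth 1 | Tooth 2 unaffected | Tooth-2 pain halved | Tooth-2 pain abolished | Patient excluded if tooth 1 injected |
|---|---|---|---|---|
| 10% | −9.3 | −7.0 | −4.8 | −10.8 |
| 20% | −9.3 | −5.1 | −0.9 | −12.1 |

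The abolished column agrees with step 3. At 10% the shift is 9.3 − 4.8 = 4.5 mm, or 4.5 / 0.10 = 45 mm lost per injected patient. At 20% it is 9.3 − 0.9 = 8.4 mm, or 8.4 / 0.20 = 42 mm. Both lie within the assumed 30 to 50 mm.

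If a patient is excluded when either tooth passes the same pain threshold, the difference is −6.9 mm with 71% of patients kept (10% case) or −5.8 mm with 54% kept (20% case). Exclusion can therefore move the result either way, depending on the unit chosen.

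**5. Cost in precision if pairs are dropped**

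Dropping 10% to 30% of 48 pairs leaves 48 × 0.90 ≈ 43 to 48 × 0.70 ≈ 34. The standardized paired difference detectable with 80% power at two-sided 5% is (1.96 + 0.84) / √n:

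- 48 pairs: 2.80 / √48 = 0.40
- 43 pairs: 2.80 / √43 = 0.43
- 34 pairs: 2.80 / √34 = 0.48

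**The case against.** The best defence is that Section 6.1.2 already deals with this. A procedure finished under injection is not included, so its overall mark never enters the analysis. In a within-patient comparison, tooth 2 then has no partner and drops out as well. If the exclusion means the whole patient, no post-injection mark is analysed at all. In addition, the VAS form is marked before anaesthetic is offered, so a clean laser-pain mark exists. Handling of data after rescue is also often left to the SAP, which is not at hand.

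Much of this stands. A reader might infer that every tooth-2 mark after an injection is invalid, that the overall mark on tooth 1 says nothing about laser pain, or that the distortion arises however Section 6.1.2 is read. The protocol supports none of these. Its text states neither a single visit nor an interval, and similar teeth need not share an anaesthetised area. The overall mark includes the pain felt before the injection. Whole-patient exclusion would remove the contamination.

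The defence does not close the gap. The unit left out is not named, and Section 4.1 makes no exception. The protocol fixes no paired analysis and judges the mode of treatment by average score, so a tooth 2 without its partner can stay in the no-LLLT average. Excluding the patient replaces contamination with pain-dependent exclusion. An SAP cannot recover which tooth was injected, or when, if this was never recorded.

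**Conclusion.** The point holds in a limited form. Sections 4.1, 6.1.2 and 7.1 do not fit together once an injection is accepted on the first tooth. The overall VAS of that tooth is a mixed measure. Under the most natural reading of Section 6.1.2 the second tooth stays in, and its VAS and hand raises may be too low.

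The size is unknown. The 3 to 15 mm fall in the mean no-LLLT VAS rests on assumed injection rates and losses, and applies only if tooth-2 data are kept and the anaesthetic still reaches that tooth. Taken alone, it would shrink the apparent benefit of LLLT. Where the injected LLLT tooth is itself dropped or scored too low, the LLLT average falls as well, so the net direction cannot be stated. It would go too far to say that the comparison is certainly biased. What can be said is that the protocol permits the bias and does not require the data needed to detect it.

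**What to change.** Reconcile Sections 4.1, 6.1.2 and 7.1 before enrolment, so that they state:

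- **Unit.** Whether an injection leaves out later marks, the tooth or the patient, and how a second tooth prepared afterwards is handled.
- **Record.** On the CRF, which tooth was injected and when.
- **Tooth injected.** The VAS mark made before the injection is that tooth's laser-pain score. Any overall mark made afterwards is kept separately. The report should say that the earlier mark rates an unfinished preparation and is not fully comparable with marks on completed teeth.
- **Tooth 2.** VAS marks, hand raises and the automatic zero do not count as injection-free laser data when collected while anaesthetic from tooth 1 may still act.
- **Outcome.** Injection is reported for each tooth as an outcome, so that these patients are not silently dropped.

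The cost is a wording change, two CRF fields, and some pairs with an incomplete tooth-2 score. Scheduling and the care given after a pain signal are for the sponsor to settle; only the status of the research marks is at issue here.
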